#### 8.1.1 Adverse (Drug) Reaction

All noxious and unintended responses to a study drug related to any dose should be considered an adverse drug reaction. "Responses" to a study drug means that a causal relationship between a study drug and an adverse event is at least a reasonable possibility, ie, the relationship cannot be ruled out.

#### 8.1.2 Unexpected Adverse Drug Reaction

An Unexpected Adverse Drug Reaction is defined as an adverse reaction, the nature or severity of which is not consistent with the applicable product information. For APX001 the reference safety information is included in the IB currently in force. The reference safety information will be reviewed yearly, and the periodicity of the review will be harmonized with the reporting period of the Development Safety Update Report.

#### 8.1.3 Assessment of Adverse Events by the Investigator

The Investigator will assess the severity (intensity) of each adverse event and will also categorize each adverse event as to its potential relationship to study drug using the categories of "yes" or "no."

#### Assessment of Severity:

The severity of all adverse events should be graded according to the CTCAE v5.0. For those adverse event terms not listed in the CTCAE, the following grading system should be used:

- CTCAE Grade 1: Mild; asymptomatic or mild symptoms; clinical or diagnostic observations only; intervention not indicated
- CTCAE Grade 2: Moderate; minimal local or noninvasive intervention indicated; limiting age-appropriate instrumental activities of daily living
- CTCAE Grade 3: Severe or medically significant but not immediately life-threatening; hospitalization or prolongation of hospitalization indicated; disabling; limiting self-care activities of daily living
- CTCAE Grade 4: Life threatening consequences; urgent intervention indicated
- CTCAE Grade 5: Death related to the adverse event

#### Causality Assessment:

The relationship of an adverse event to the administration of the study drug is to be assessed according to the following definitions:

No (not related, unlikely to be related) – The time course between the administration of study drug and the occurrence or worsening of the adverse event rules out a causal relationship and another cause (concomitant drugs, therapies, complications, etc) is suspected.

Yes (possibly, probably, or definitely related) – The time course between the administration of study drug and the occurrence or worsening of the adverse event is consistent with a causal relationship and no other cause (concomitant drugs, therapies, complications, etc) can be identified.

The definition implies a reasonable possibility of a causal relationship between the event and the study drug. This means that there are facts (evidence) or arguments to suggest a causal relationship.

The following factors should also be considered:

• The temporal sequence from study drug administration-

The event should occur after the study drug is given. The length of time from study drug exposure to event should be evaluated in the clinical context of the event.

• Underlying, concomitant, intercurrent diseases-

Each report should be evaluated in the context of the natural history and course of the disease being treated and any other disease the patient may have.

• Concomitant drug-

The other drugs the patient is taking or the treatment the patient receives should be examined to determine whether any of them might be recognized to cause the event in question.

• Known response pattern for this class of study drug-

Clinical and/or preclinical data may indicate whether a particular response is likely to be a class effect.

• Exposure to physical and/or mental stresses-

The exposure to stress might induce adverse changes in the recipient and provide a logical and better explanation for the event.

• The pharmacology and PK of the study drug-

The known pharmacologic properties (absorption, distribution, metabolism, and excretion) of the study drug should be considered.

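### Protocol 8.1.3 defines a related event as one with no other identifiable cause, which contradicts its own label and the reasonable-possibility standard of 8.1.1, and leaves a common case without a code

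*Protocol*

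**What the plan says.** Protocol 8.1.3 asks the investigator to "categorize each adverse event as to its potential relationship to study drug using the categories of" yes or no. No third category and no default is given. The Causality Assessment part then defines each code by two conditions joined by *and*:

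- *Yes*, labelled "Yes (possibly, probably, or definitely related": the time course "is consistent with a causal relationship and no other cause (concomitant drugs, therapies, complications, etc) can be identified".
- *No*, labelled "No (not related, unlikely to be related": the time course "rules out a causal relationship and another cause (concomitant drugs, therapies, complications, etc) is suspected".

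The text that follows says the definition implies a reasonable possibility of causality, and explains: "This means that there are facts (evidence) or arguments to suggest a causal relationship". A list of factors to consider comes next. It includes underlying and intercurrent disease, and other drugs, which are to be "examined to determine whether any of them might be recognized to cause the event in question". The list does not say which code follows when such a cause is found.

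Protocol 8.1.1 defines an adverse drug reaction by a different test: "a causal relationship between a study drug and an adverse event is at least a reasonable possibility, ie, the relationship cannot be ruled out".

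Relatedness is then used in four places: the study discontinuation criterion (Synopsis, Withdrawal Criteria; Protocol 4.4.1), SAE reporting after the Follow-Up Visit (Protocol 8.3), the tabulation of events by relationship (Protocol 9.2.2) and the related-event summaries (SAP 6.8.8). SAP Appendix 3 spells out the abbreviation TRAE, but the SAP does not say what counts as related.

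**The concern.** The two codes are not complements, and the condition that breaks them apart is one that many events in this trial could meet. The host factors in Protocol Appendix E include hematologic malignancy, transplant and immunosuppressive treatment. Protocol 1.2.1 lists headache, dizziness, fatigue, nausea, vomiting and liver toxicity as potential risks of the drug. In such patients these events can readily have another identifiable cause. Protocol Section 1 shows this for the earlier study in AML patients, where clinically significant abnormal findings were attributed to the leukemia and its chemotherapy.

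Two investigators who both follow the protocol can therefore code the same event differently. One reads the no-other-cause clause literally and does not record *Yes*. The other follows the reasonable-possibility sentence and does. The trial has no concurrent control, so there is no comparator rate against which to judge inconsistent attribution. At stake are the related-event tables, the count of patients toward the discontinuation criterion, and whether an SAE after the Follow-Up Visit is reported.

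**Working it through.** The documents state no figure on this point, so there is nothing to reproduce. The check compares the texts.

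**Step 1. Apply the 8.1.3 definitions literally.** *No* speaks of a cause that is suspected and *Yes* of a cause that can be identified, so these are kept apart. For the last column I assume that timing alone decides whether causality can be ruled out.

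| Timing | Other cause | Code under 8.1.3, read literally | Reaction under 8.1.1 |
|---|---|---|---|
| Compatible | None | Yes | Yes |
| Compatible | Suspected only | Yes (nothing identified) | Yes |
| Compatible | Identified | **Neither definition met** | Yes |
| Excludes causality | None | Neither definition met | No |
| Excludes causality | Suspected | No | No |
| Excludes causality | Identified | No | No |

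**Step 2. Separate the real gap from the wording gap.** In row 4 the label of *No* includes events that are not related, and 8.1.1 counts only events that cannot be ruled out. Both point to *No*, so this row is loose wording and not a practical ambiguity. In row 3 nothing settles the code. The label *possibly*, the reasonable-possibility sentence and 8.1.1 all point to *Yes*; the definition of *Yes* forbids it; and *No* is not met because timing does not exclude causality.

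**Step 3. Direction.** If the clause is applied as a bar to *Yes*, row 3 events are not counted as related although 8.1.1 would count them. No row moves the other way. The literal reading can therefore only lower the number of related events relative to 8.1.1.

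**Step 4. Trace what depends on the code.**

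- Affected: relationship tables (Protocol 9.2.2, SAP 6.8.8); the criterion of five or more patients with the same related event of Grade 2 or worse (Synopsis, Protocol 4.4.1), under which the study may be stopped; and SAEs after the Follow-Up Visit, which are reported only if considered related (Protocol 8.3).
- Not affected: recording of all adverse events (Protocol 8.1), all-causality tables, SAE reporting from first dose to the Follow-Up Visit (Protocol 8.3), DSMB powers (Protocol 4.4.1, 9.2.5) and all-cause mortality through Day 42 (Protocol 7.1).

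**Step 5. Size.** A size would need the share of events with compatible timing and an identified rival cause, and the share of those not coded *Yes*. The documents give neither.

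**The case against.** The best reply is that the clause should not be read alone. The sentence after the definitions asks for a reasonable possibility, and the factor list tells investigators to weigh other diseases and drugs. That weighing would have little purpose if any rival cause automatically barred *Yes*. Most of 8.1.3 therefore leans toward 8.1.1, and many investigators will code accordingly. This is fair, but it does not remove the problem. The protocol says relationship is to be assessed by the stated definitions, so literal application is compliant, and no text gives the code once a rival cause has been identified. An eCRF completion guide may do so, but none is among the documents.

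Three stronger readings are tempting and are not supported:

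- A reader might infer that the scheme fails for two kinds of event, because two rows of the table meet neither definition. Only the row with compatible timing and an identified cause is a real ambiguity; the other is resolved by the *No* label and 8.1.1.
- A reader might infer that expedited reporting is narrowed. Protocol 8.5 speaks of adverse reactions, the concept defined in 8.1.1, and gives the task to the sponsor or its designee. Nothing there makes the investigator's yes/no code decisive.
- A reader might take the five-patient threshold as a measure of harm, since one patient's coding can separate four from five. That is true of any count threshold. The criterion is also discretionary, and the DSMB can act on other signals.

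The lack of a definition of related in the SAP is not an error in itself, since relatedness is assessed under the protocol. It does mean that the SAP inherits the conflict.

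**Conclusion.** The point holds for one defined case. The *Yes* definition in Protocol 8.1.3 contradicts its own label, the reasonable-possibility sentence in the same section and the definition in 8.1.1. As a result, an event with compatible timing and an identified alternative cause has no valid code. Applied literally, the rule yields fewer related events than 8.1.1 would. The conflict and its direction follow from the text; how often it will matter cannot be derived from the documents, and no size is claimed. That such events will be common is a judgement from the population described. The conclusion assumes that no coding instruction outside the documents already settles the case. The point bears on the interpretation of related events, not on the primary efficacy result or on the recording of adverse events. It deserves correction because a stated rule gives conflicting instructions and the correction is small.

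**What to change.** In Protocol 8.1.3:

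- Delete the no-other-cause condition from *Yes*. Define *Yes* as a reasonable possibility of a causal relationship, whether or not another cause is also possible.
- Define *No* as the complement: no reasonable possibility, whether or not another cause is suspected. Every event then has exactly one code.
- Keep the factor list as input to the judgement.

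Leave 8.1.1 unchanged. Narrowing its cannot-be-ruled-out wording to the facts-or-arguments test could reduce what counts as a reaction for expedited reporting under 8.5. Some difference in emphasis between the *unlikely* label in 8.1.3 and that wording will remain, but both sections will then rest on reasonable possibility.

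In SAP 6.8.8, have the related-event summaries refer to the revised definition. If an eCRF completion guide exists, it must match.

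The cost is a few lines of protocol text and one SAP cross-reference. The downside is that more background events in these seriously ill patients will be coded related, so the discretionary discontinuation criterion may be met more often. The all-causality tables will help readers judge related-event counts in that light.

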#### 8.2 Serious Adverse Events

An adverse event or adverse reaction is considered serious if, in the view of either the Investigator or Sponsor, it results in any of the following outcomes:

- Death.
- A life-threatening adverse event.

**Note**: An adverse event or adverse reaction is considered "life-threatening" if, in view of either the Investigator or Sponsor, its occurrence places the patient at immediate risk of death. It does not include an event that, had it occurred in a more severe form, might have caused death.

• Requires hospitalization or prolongation of existing hospitalizations.

**Note:** Any hospital admission with at least one overnight stay will be considered an inpatient hospitalization. An emergency room or urgent care visit without hospital admission will not be recorded as a SAE under this criterion, nor will hospitalization for a procedure scheduled or planned before signing of informed consent, or elective treatment of a pre-existing condition that did not worsen from Baseline. However, unexpected complications and/or prolongation of hospitalization that occur during elective surgery should be recorded as adverse events and assessed for seriousness. Admission to the hospital for social or situational reasons (ie, no place

to stay, live too far away to come for hospital visits, respite care) will not be considered inpatient hospitalizations.

- A persistent or significant disability/incapacity or substantial disruption of the ability to conduct normal life functions.
- A congenital anomaly/birth defect.
- An important medical event.

**Note:** Important medical events that do not meet any of the above criteria may be considered an SAE when, based upon appropriate medical judgment, they may jeopardize the patient and may require medical or surgical intervention to prevent one of the outcomes listed above. Examples of such medical events include allergic bronchospasm requiring intensive treatment in an emergency room or at home, blood dyscrasias or convulsions that do not result in inpatient hospitalizations, or the development of drug dependency.

# 8.3 Serious Adverse Event Reporting – Procedures for Investigators

#### Initial Reports

All SAEs occurring from the time of initial dosing until the Follow-Up Visit must be reported to Medpace Clinical Safety within 24 hours of the knowledge of the occurrence (After the Follow-Up Visit, any SAE that the Investigator considers related to study drug must be reported to the Medpace Clinical Safety or the Sponsor/designee).

To report the SAE, complete the SAE form electronically in the electronic data capture (EDC) system for the study. When the form is completed, Medpace Safety personnel will be notified electronically by the EDC system and will retrieve the form. If the event meets serious criteria and it is not possible to access the EDC system, send an email to Medpace Safety at [contact] or call the Medpace SAE reporting line (phone number listed below), and fax/email the completed paper SAE form to Medpace (contact information listed in Section 8.6) within 24 hours of awareness. When the EDC system becomes available, the SAE information must be entered within 24 hours of the system becoming available.

Safety Contact Information: Medpace Clinical Safety Medpace SAE reporting line – USA: [contact], dial 3 or [contact], dial 3 [contact] or [contact] Email: [contact]

Medpace SAE reporting line – Europe: [contact] [contact] Email: [contact]

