# 6.3.9 Day 42 (± Days)

If EOST procedures are performed after Day 39, Day 42 procedures will not be required. The following procedures will be performed on Day 42 ( $\pm 2$  days):

- Administer 600 mg APX001 by IV infusion over 3 hours QD or 800 mg APX001 PO QD.
- Record Investigator assessment of global response.
- Assess survival status.
- Perform urine or serum pregnancy test on women of childbearing potential only.
- Perform a complete physical examination including assessment of general appearance, skin, eyes, heart, chest, abdomen, and a neurological examination and measure weight.

- Assess clinical signs and symptoms.
- Record vital signs, including temperature, blood pressure, heart rate, respiratory rate, and oxygen saturation.
- Perform 12-lead ECG in triplicate.
- Perform clinical laboratory assessments (serum chemistry, hematology [including CBC with differential], coagulation [including PT/INR], and urinalysis).
- Perform CT scan if clinically indicated.
- Collect serum samples for analysis of CCI and C.
- Collect samples for fungal cultures (eg, from BAL fluid, sputum, bronchial brush, sinus aspirate, tracheal aspirate) as clinically indicated.
- Collect BAL samples per SOC for culture and CCI testing as clinically indicated.
- Collect plasma PK samples predose for IV dosing or at any time in clinic for PO dosing.
- Record concomitant medications.
- Assess adverse events.
- Review accountability for all returned study drug.

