# 7 EFFICACY ASSESSMENTS

#### 7.1 Primary Efficacy Endpoint

The primary efficacy parameter is the following:

• All-cause mortality through Day 42.

**Note:** All-cause mortality will represent the percentage of patients who die after the first dose of study drug through Day 42 from any cause.

Every attempt must be made to record survival status at Day 42 or anytime thereafter for all dosed patients, regardless of their status of treatment, as long as the patient has not withdrawn consent from participation in the study. An in-person assessment is preferred; however, this assessment may also be performed via a telephone call if an in-person visit is not possible.

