#### 8 SAFETY ASSESSMENTS

#### 8.1 Adverse Events

An adverse event is defined as any untoward medical occurrence in a clinical investigation patient administered a pharmaceutical product, which does not necessarily have a causal relationship with this treatment. An adverse event can therefore be any unfavorable and/or unintended sign (including an abnormal laboratory finding), symptom, or disease temporally associated with the use of an IMP, whether or not related to the IMP. All adverse events, including observed or volunteered problems, complaints, or symptoms, are to be recorded on the appropriate eCRF.

Adverse events, which include clinical laboratory test variables, will be monitored and documented from the time of initial dosing through the Follow-Up Visit. Patients should be instructed to report any adverse event that they experience to the Investigator, whether or not they think the event is due to study treatment. Following initial dosing, Investigators should make an

assessment for adverse events at each visit and record the event on the appropriate adverse event eCRF.

Wherever possible, a specific disease or syndrome rather than individual associated signs and symptoms should be identified by the Investigator and recorded on the eCRF. However, if an observed or reported sign or symptom is not considered a component of a specific disease or syndrome by the Investigator, it should be recorded as a separate adverse event on the eCRF. Additionally, the condition that led to a medical or surgical procedure (eg, surgery, endoscopy, tooth extraction, or transfusion) should be recorded as an adverse event, not the procedure itself.

Any medical condition already present at initial dosing should be recorded as medical history and not be reported as an adverse event unless the medical condition or signs or symptoms present at Baseline changes in severity, frequency, or seriousness at any time during the study. In this case, it should be reported as an adverse event.

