a. Administration of APX001 should not continue for longer than 6 weeks. If an Investigator documents an improvement or resolution in clinical signs and symptoms prior to 6 weeks, eg, if follow-up imaging (as applicable) shows improvement; or a mycological response (if amenable to repeat sampling) is observed, the Investigator may choose to discontinue dosing. Patients will be requested to return for an EOST and Follow-Up Visit and to agree to a Follow-Up Phone Call.

b. During the Treatment Period, outpatients will be asked to record daily dosing on a diary and bring the diary and study drug bottles with them to every clinic visit.

- c. If EOST procedures are performed after Day 39, Day 42 procedures will not be required.
- d. The EOST will occur within 2 days of completion of APX001 dosing.
- e. The Follow-Up Visit will occur 4 weeks (±3 days) post EOST. The Follow-Up Phone Call will occur 12 weeks (±3 days) after Day 1 (Baseline).

f. Cohort A: Historical patient EORTC/MSGERC classification of proven or probable IMI may be used for study assessment.

g. Assess disease severity using the Eastern Cooperative Oncology Group Performance Status and Karnofsky Performance Status. Assess P/F ratio (if patient is ventilated)

- h. For females of childbearing potential only.
- i. If the Screening Visit occurred  $\geq$ 96 hours prior to Day 1 (Baseline), perform a urine or serum pregnancy test on women of childbearing potential only.
- j. Conduct a complete physical examination. The physical examination includes an assessment of general appearance, skin, eyes, heart, chest, abdomen, and a neurological examination. Measure height only at Screening. Measure weight at each indicated visit.
- k. Conduct a neurological examination (all patients) and a symptom-directed physical examination as clinically indicated (ie, new signs or symptoms and follow-up on earlier findings). Measure weight at each indicated visit.
- 1. Assessment of clinical signs and symptoms includes examination of the following body systems: general appearance including skin, head, eyes, ears, nose, throat, neck, trunk, lymph nodes, respiratory, cardiovascular, gastrointestinal, genitourinary, musculoskeletal, neurological, psychological, lymphatic/hematological, and endocrine/metabolic.

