3.7. Adverse Events

An adverse event is defined as any untoward medical occurrence in a clinical investigation patient administered a pharmaceutical product, which does not necessarily have a causal relationship with this treatment. An adverse event can therefore be any unfavorable and/or unintended sign (including an abnormal laboratory finding), symptom, or disease temporally associated with the use of an IMP, whether or not related to the IMP. Any adverse event that started on or after the administration of study drug will be considered a treatment emergent adverse event (TEAE). AEs will be captured from the time of initial dosing through the Follow-Up Visit. Events that occur after Day 42 (maximum duration of treatment with fosmanogepix) but prior to and including the Follow-Up visit will be considered treatment

emergent. All AEs will be coded to system organ class (SOC) and preferred term (PT) using the MedDRA.

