6.8.8. Adverse Events

An overview of AEs will be provided including counts and percentages of patients (and event counts) with the following:

- Any AEs.
- Any TEAEs (overall and by maximum severity).
- Any study drug related TEAEs (overall and by maximum severity).
- Any serious AEs (SAEs).
- Any treatment-emergent SAEs (TESAEs).
- Any TRSAEs).
- Any TEAEs leading to discontinuation of study drug.
- Any TRAEs leading to discontinuation of study drug.
- Any AEs leading to death.

The number and percentage of patients who experienced at least one TEAE will be presented by SOC and PT. TEAEs, TRAEs, study drug withdrawals due to TEAEs and TRAEs, and all SAEs will be summarized in the same manner.

Summaries will be provided by worst grade for the number and percentage of patients with TEAEs and TRAEs by SOC and PT.

Although a patient may have two or more TEAEs, the patient is counted only once within a SOC and PT category. The same patient may contribute to two or more PTs in the same SOC category.

A list of patients who have SAEs, a list of patients who discontinue from study drug due to TEAEs or TRAEs, and a list of death due to AEs will be provided. All AEs will be listed.

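### For patients whose last dose falls in about the first two weeks, routine SAE reporting can close before Day 42, so a death judged unrelated can count in the primary endpoint without an SAE report or a cause.

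*Protocol*

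**What the plan says.** **Safety window.** Protocol 8.1 states that adverse events "will be monitored and documented from the time of initial dosing through the Follow-Up Visit". SAP 3.7 repeats this: "AEs will be captured from the time of initial dosing through the Follow-Up Visit". Protocol 8.3 sets the same limits for SAEs: "All SAEs occurring from the time of initial dosing until the Follow-Up Visit must be reported". Beyond that point the duty narrows: "After the Follow-Up Visit, any SAE that the Investigator considers related to study drug must be reported".

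**Where the window ends.** Appendix A, footnote e: "The Follow-Up Visit will occur 4 weeks (±3 days) post EOST". Protocol 6.4 places EOST within 2 days of the last dose. Dosing may stop before 6 weeks for improvement (3.1, 5.5.3), for lack of response or an adverse event (4.4.2), or because a prohibited antifungal is needed (4.3). No minimum duration is given.

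**Endpoint window.** Protocol 7.1: "All-cause mortality will represent the percentage of patients who die after the first dose of study drug through Day 42 from any cause". The same section requires survival status at Day 42 or later to be sought for all dosed patients whatever their treatment status, unless consent is withdrawn.

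**Day 42 visit.** Protocol 6.3.9: "If EOST procedures are performed after Day 39, Day 42 procedures will not be required". The procedures listed there include both survival status and adverse event assessment.

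**Reporting of deaths.** SAP 6.8.8 counts patients with AEs leading to death and says "a list of death due to AEs will be provided". It plans no listing of all deaths.

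**The concern.** The safety window is counted from the end of treatment and the endpoint window from first dose, and nothing aligns them. When treatment ends early enough, the first closes before the second. A death in between is found through the survival check, but that check asks only for status. If the investigator does not consider the event related, no SAE form, cause or relatedness entry is required, and the death can be absent from the SAP list of deaths due to AEs.

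Some patients who stop in the first two weeks will have stopped for failure or intolerance. Their deaths are among those a reader of a small single-arm mortality trial will most want explained. SAP 3.7 discusses events after Day 42 and up to the Follow-Up Visit, but not a Follow-Up Visit that comes first, so the case appears to have been overlooked.

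There is also an inconsistency. Read literally, 6.3.9 keeps the Day 42 adverse event assessment for a patient whose EOST was on or before Day 39. For the earliest stoppers, 8.1 and 8.3 have already closed the window by then.

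**Working it through.** **1. The plan's own figure.** No stated figure depends on this point. The sample size was reproduced to check the endpoint. With 24 mITT patients, the exact one-sided test of 45% rejects at 7 or fewer deaths. The attained alpha is 0.0863, and power at 20% mortality is 0.9108, which agrees with the stated >90%. Also 24 / 0.6 = 40 dosed. None of this changes under the fix.

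**2. When the Follow-Up Visit falls.** Let L be the study day of the last dose.
- EOST = L + 0 to 2 days (Protocol 6.4).
- Follow-Up Visit = EOST + 28 ± 3 days (Protocol 6.5).
- Earliest: L + 0 + 28 − 3 = L + 25. Nominal (EOST on the last-dose day, visit on time): L + 28. Latest: L + 2 + 28 + 3 = L + 33.
- Uncovered days = max(0, 42 − Follow-Up day).

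| Last dose (day) | Follow-Up Visit: earliest / nominal / latest | Uncovered days: earliest / nominal / latest |
|---|---|---|
| 1 | 26 / 29 / 34 | 16 / 13 / 8 |
| 5 | 30 / 33 / 38 | 12 / 9 / 4 |
| 7 | 32 / 35 / 40 | 10 / 7 / 2 |
| 8 | 33 / 36 / 41 | 9 / 6 / 1 |
| 9 | 34 / 37 / 42 | 8 / 5 / 0 |
| 10 | 35 / 38 / 43 | 7 / 4 / 0 |
| 13 | 38 / 41 / 46 | 4 / 1 / 0 |
| 14 | 39 / 42 / 47 | 3 / 0 / 0 |
| 16 | 41 / 44 / 49 | 1 / 0 / 0 |
| 17 | 42 / 45 / 50 | 0 / 0 / 0 |
| 21 | 46 / 49 / 54 | 0 / 0 / 0 |

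The gap is certain for a last dose by Day 8, depends on the windows for Days 9 to 16, and is absent from Day 17. At nominal timing it affects a last dose by Day 13.

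**3. How many deaths.** The documents do not give the number of early stoppers. Assumptions: 4 to 10 of 40 dosed patients have a last dose on Day 5 (nominal Follow-Up Day 33, 9-day gap); the hazard is constant at the plan's two mortality rates; 60% of dosed patients enter the mITT Population.
- At 45% mortality: hazard = −ln(0.55)/42 = 0.0142 per day. Survival to Day 33 = exp(−0.0142 × 33) = 0.63. Risk over 9 days = 1 − exp(−0.0142 × 9) = 0.12.
- At 20% mortality: hazard = −ln(0.80)/42 = 0.0053 per day. Survival to Day 33 = 0.84. Risk over 9 days = 0.047.
- Upper: 10 × 0.6 × 0.63 × 0.12 = 0.45 deaths. Lower: 4 × 0.6 × 0.84 × 0.047 = 0.09 deaths.

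These figures include deaths judged related and deaths from SAEs already open, both of which are reportable, so fewer would go unreported under the same assumptions.

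**The case against.** A safety window based on exposure, alongside an endpoint window based on first dose, is a legitimate choice, and several provisions narrow the gap.

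- **Open SAEs.** Under Follow-Up Reports in 8.3, an SAE is followed until it subsides, becomes chronic, stabilizes or the patient dies, and the form is updated. SAP 6.8.8 sets no cut-off on date of death. A patient stopped for a serious event that is unresolved and later fatal is therefore covered. This stands, and confines the gap to events that start after the Follow-Up Visit.
- **Related SAEs.** The duty to report these after the Follow-Up Visit has no time limit, so a later causality judgement still triggers a report. This stands too. It does not reach events judged unrelated, and under the causality definitions in 8.1.3 a Yes requires that no other cause can be identified. In seriously ill patients another cause can often be named.
- **Day 42 visit.** Read literally, 6.3.9 provides an adverse event check. But its list also includes dosing, so whether it applies off treatment is unclear. If it does, it conflicts with 8.1 and 8.3; if it does not, the gap remains.

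A reader might also infer more than the documents support. Stopping early does not in itself create a gap, since a last dose from Day 17 leaves none. The primary result loses no deaths, because 7.1 requires survival status to be sought for every dosed patient. Whether the DSMB would miss these deaths cannot be judged without its Charter. Efficacy and safety death counts will differ anyway, because efficacy uses mITT through Day 42 and safety uses all dosed patients over another period.

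**Conclusion.** The point holds for patients whose last dose is in about the first two weeks. For them, a new fatal event that starts after the Follow-Up Visit and by Day 42, and that the investigator does not consider related, counts in the primary endpoint. It has no mandatory SAE report, no section asks for its cause, and it can be absent from the SAP list of deaths due to AEs. Protocol 6.3.9 also needs reconciling with 8.1 and 8.3.

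The expected size is small: about 0.1 to 0.45 primary-endpoint deaths under the assumptions above. The result scales with the number of early stoppers, for which the documents give no basis. It also assumes that early stoppers die at the average rate, whereas those stopped for failure may do worse and those stopped for improvement better. The test, the sample size and the mortality estimate are unaffected. This is an inexpensive improvement to the safety record, and does not invalidate the efficacy analysis.

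**What to change.** 1. In Protocol 8.1 and 8.3 and SAP 3.7, end AE and SAE collection at the later of the Follow-Up Visit and Day 42. This also reconciles the Day 42 assessment in 6.3.9 with the collection window.
2. Record date, cause and relatedness for every death through Day 42.
3. In SAP 6.8.8, list all deaths through Day 42, not only those due to AEs, so that each death in the primary endpoint can be traced in the safety output.

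The cost is about one sentence in each section and, if the survival form does not already hold them, fields for cause and relatedness. The downside is up to about two more weeks of adverse event recording (13 days nominally, 16 at most) in the few patients who stop very early, at a Day 42 survival contact that 7.1 already requires.
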